14.2 Correlative Endpoints Statistical Considerations

The study is not powered to detect specific hypotheses; rather this data and analysis will help better identify patients having the potential to benefit from this therapy and aid in designing larger Phase III studies.

- I. To investigate the rate of seroconversion in patients HSV seronegative at baseline after initial intralesional infusion of talimogene laherparepvec. The rate of

seroconversion, after initial intralesional infusion of talimogene laherparepvec, in patients HSV seronegative at baseline will be reported using descriptive statistics.

II. To evaluate associations between selected biomarkers measured in serial peripheral blood over time with clinical efficacy, including immunophenotyping and functional analyses, evaluation of serum levels of chemokines, cytokines and other immune mediators, and characterization of T-cell receptor clonality in peripheral blood. Summary statistics will be used to for describing changes across time. In addition the time course of biomarker measurements will be investigated graphically, by summary plots or individual patient plots; their trends over time will be categorized either by visual inspection (if there are clear trend groups such as monotonically increasing or monotonically decreasing) or by pattern recognition methods such as K-means clustering. The associations with the observed trend in selected biomarkers analyzed will be evaluated using categorical data analysis (including Fisher's exact test and logistic regression) for clinical outcome such as response and clinical benefit, and using survival data analysis (including Kaplan-Meier curve and Cox Proportional Hazards models) for survival outcomes such as progression-free survival and survival.

III. To assess the potential effect of talimogene laherparepvec cell lysis and pembrolizumab on selected biomarker expression measured in pre- and post-treatment tumor tissue and the association between these biomarkers and with clinical outcome, including characterization of PD-1/PD-L1 expression, tumor infiltrating lymphocytes (TILs) and tumor antigens, gene expression profiling, and characterization of T-cell receptor clonality in tumor-infiltrating lymphocytes (TIL). The pre- and post-treatment measurements will be compared using the paired t-test for each of these biomarkers. The associations with the selected biomarkers, in terms of both the pre-treatment measurement and the difference between pre- and post-treatment measurements, will be evaluated using the two-sample t-test for clinical outcome such as response and clinical benefit, and using survival data analysis (including Kaplan-Meier curve and Cox Proportional Hazards models) for survival outcomes such as progression-free survival and survival. More specifically, Kaplan-Meier curve and Cox Proportional Hazards models will be used for analyzing pre-treatment measurement; Kaplan-Meier curve at a landmark time point and Cox Proportional Hazards models allowing for time varying coefficients will be used for analyzing the difference between pre-and post treatment measurements.

IV. To evaluate the association between baseline tumor mutational burden and neoantigen production with clinical efficacy of the study therapy.

The associations with baseline tumor mutational burden and neoantigen production will be evaluated using categorical data analysis (including Fisher's exact test and logistic regression) for clinical outcome such as response and clinical benefit, and using survival data analysis (including Kaplan-Meier curve and Cox Proportional Hazards models) for survival outcomes such as progression-free survival and survival.

V. To evaluate pre and posttreatment magnetic resonance Images of the recurrent, resectable, sarcoma in patients in enrolled in the additional neoadjuvant cohort, to assess for definable radiological changes that can be correlated with treatment response

Summary statistics will be used to for describing changes across time. The associations between radiological changes and treatment response (clinical and pathological) will be evaluated using categorical data analysis (including Fisher's exact test and logistic regression).

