4.0 OVERVIEW OF STUDY DESIGN/INTERVENTION

4.1 Design

This is a single-center, single-arm phase II clinical trial with additional cohorts to evaluate efficacy, as assessed by response rate, of the oncolytic herpes virus talimogene laherparepvec given in combination with the anti-PD1 monoclonal antibody pembrolizumab for patients with metastatic and/or locally advanced sarcomas.

Patients will initiate treatment with talimogene laherparepvec given intralesionally and pembrolizumab. Talimogene laherparepvec treatment will be given at Day 1 Week 1, and every 3 weeks thereafter. (Table 1). Pembrolizumab will be given at Day 1 week 1 and every

3 weeks thereafter (Table 1). Patients will be reassessed at week 8 and every 8 weeks thereafter.

Patients will be evaluated radiographically at baseline, week 8 (+/- 7 days) and every 8 weeks (+/- 7 days) subsequently until week 56 and then every 12 weeks thereafter or as per the discretion of the treating investigator. Response will be assessed using RECIST v1.1 (primary response assessment) and immune-related response criteria (irRECIST) (secondary response assessment).

The study will be sequentially monitored for pre-defined treatment-related toxicity events based on an early stopping rule as detailed in section 11. All study participants where feasible will undergo mandatory tumor biopsies, at baseline and week 8, of a distant site of disease. A site not intended to be injected is preferred for biopsy where feasible. Optional biopsies at progression will be offered. Serial blood samples will be obtained at baseline, during, and after treatment. Talimogene laherparepvec and pembrolizumab dosing should continue provided that the subject has no evidence of confirmed PD within 8 weeks of initial PD per RECIST, has no clear clinical deterioration and is able to tolerate the treatment. Treatment beyond progression will be allowed as long as patient is clinically benefitting, is tolerating the drug well and continues to meet all study treatment criteria.

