Subjects with a complete response (CR) may stop injections of talimogene laherparepvec, but treatment with pembrolizumab will be continued unless one of the criteria for treatment discontinuation is met. This is discussed in again in section 13.0.

Due to the mechanism of action, subjects may experience growth in existing tumors or the appearance of new tumors prior to maximal clinical benefit of talimogene laherparepvec and pembrolizumab. The patient may be allowed to continue study treatment after initial RECIST 1.1 defined progression if they are assessed by the treating physician to be deriving clinical benefit and tolerating study treatment. The treating physician may consult with the overall study PI for help with assessing the patient. Such patients should discontinue study therapy upon further evidence of progression.

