10.0 EVALUATION DURING TREATMENT/INTERVENTION

10.1 – Pre-treatment diagnosis confirmation

All patients will have histological confirmation of their diagnosis prior to treatment. Baseline clinical and radiologic evaluations are to be conducted within 3 weeks of starting protocol therapy. In addition, a mandatory baseline biopsy will be performed within 30 days of first dose of the study drugs for all patients enrolled in the study where feasible.

10.2 – Standard evaluations

Locally advanced/metastatic cohort

Evaluations at clinic visits will occur at weeks 1 and 4 (\pm 3 days), and then prior to every scheduled treatment (\pm 3 days) thereafter. Patients who achieve response/stability of disease lasting for at least 12 months and come off study therapy will be followed every 2 months (\pm 2 weeks) thereafter. Imaging studies will be performed at baseline, week 8 and every 8 weeks subsequently (\pm 1 week window) until 56 weeks, and then every 12 weeks thereafter or as per the discretion of the treating investigator. The clinical evaluations are delineated further in the study calendar (Table 6) and include:

- Full medical history, physical exam, assessment of performance status by KPS or ECOG status
- Review of concomitant medications
- Complete vital signs (pulse, blood pressure, temperature, respiratory rate) as well as weight and height. Height may be documented at any time prior to registration.

All patients will undergo a baseline staging CT scan of the chest (with or without contrast), abdomen and pelvis (with contrast where renal function permits), and MRI abdomen/pelvis (with and without contrast) if deemed necessary by the treating physician. Response evaluations will occur at week 8 and every 8 weeks subsequently (\pm 1 week window) until 56 weeks, and then every 12 weeks thereafter or as per the discretion of the treating investigator. EKGs will also be performed at baseline, week 8 and every 8 weeks thereafter to evaluate the heart during the study.

Routine/standard blood samples will be obtained at screening, weeks 1, 4 and then prior to every scheduled treatment (\pm 3 days) thereafter. All routine blood samples should be obtained prior to the daily dose talimogene laherparepvec and/or pembrolizumab. These samples will be used for routine tests and are part of standard of care. The following analyses will be assessed at various time points during the study:

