10.2.1 Required Laboratory Parameters for Treatment

A new dose of therapy may be initiated provided that the patient meets the following criteria within 72 hours of treatment:

- ANC \geq 1,000/ μ L

- Platelets > 75,000/ μ L
- All grade \geq 2 non-hematologic adverse events (except for fatigue, nausea and vomiting, or laboratory values that are not clinically significant) must have resolved to CTCAE grade \leq 1
- No evidence of infection/necrosis or local complications in the injection site.

10.3 – Tumor and blood samples for correlative/companion studies

All patients enrolled on this study will undergo paired biopsies/blood samples for research purposes (correlative/companion studies)

Metastatic/inoperable, locally advanced cohort:

Blood samples for research purposes will be obtained at week 1, 4, 7, 13, 19, 22 and at the date of the off study visit (\pm 7 days). This is detailed in Table 6 (Study calendar).

Biopsies for research purposes will be done at baseline (within 30 days of the first dose of talimogene laherparepvec and/or pembrolizumab) and at Week 8 in all patients enrolled in this study where feasible. Biopsy of a distant site of disease at each biopsy timepoint will be obtained. A site not intended to be injected is preferred for biopsy where feasible. Up to 6 cores from each tumor biopsy site should be taken where feasible and safe to do so. A goal of 6 cores should be obtained with a minimum of one formalin-fixed, one fresh and one flash frozen in liquid nitrogen. Biopsy procedures will otherwise be performed in accordance with institutional guidelines and the biopsy guideline outlined in Appendix F. An optional biopsy of a distant site of disease will be offered to all patients at the time of progression.

Neoadjuvant cohort:

Blood samples for research purposes will be obtained at week 1, 4, and week 6 and 12 (where applicable) prior to surgical resection. For patients receiving additional cycles of treatment, additional blood samples will be drawn prior to each cycle.

Mandatory biopsies for research purposes will be done at baseline (within 30 days of the first dose of talimogene laherparepvec and/or pembrolizumab) and at Week 4 prior to the administration of study therapy. For patients receiving additional cycles of treatment, additional core biopsies may be obtained prior to each additional treatment (ie. week 7 and week 10, etc.)

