8. Exposure cases to be reported during the duration of the study and for 30 days post treatment. If the exposed individual is reporting signs or symptoms suspected to be related to talimogene laherparepvec exposure, the exposed individual may be asked to have a swab taken at baseline, during treatment and in follow-up to evaluate for the presence of talimogene laherparepvec DNA in the suspected herpetic lesion by qPCR testing.
9. Hepatitis serology includes testing for HCV antibody, HBV core antibody and HBV surface antigen.
10. The off study visit will take place 30 days (+7 days) after the last dose of talimogene laherparepvec or the last dose of pembrolizumab, whichever is later .
11. Additional imaging for research purposes will be performed in patients with cutaneous disease. Research imaging techniques will be performed at baseline and prior to treatment biopsies and then regularly in conjunction with the schedule when standard cross sectional imaging is performed.

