12.10 Progression-Free Survival (PFS)

PFS is defined as the period from start of study treatment until recurrent or progressive of disease (POD) is objectively documented (taking as reference for progressive disease the smallest measurement recorded on study), death, or date of last evaluable tumor assessment

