12.11 Overall Survival (OS)

OS is defined as the observed length of life from start of study treatment to death or the date of last contact.

12.12 Secondary Response Criteria – Modified immune-related response evaluation Criteria in Solid (irRECIST)

Immune related RECIST (irRECIST)

In 2013, Nishino et al. demonstrated that immune-related response criteria using unidimensional measurements were highly concordant with the bidimensional results of irRC, but with less measurement variability. Based on these findings and in order to utilize

both the established criteria of irRC and RECIST 1.1, the two systems have been adapted, modified, and combined into the Immune-related Response Evaluation Criteria in Solid Tumors (irRECIST). The adapted irRECIST criteria are modifications to the irRC, incorporating the findings of Nishino et al. and the advantages of RECIST 1.1 while overcoming the shortcomings of each of the other guidelines.

irRECIST

Immune-related RECIST (irRECIST) guidelines according to Bohnsack et al. are presented below.

I. Baseline Assessments in irRECIST

In irRECIST, baseline assessment and measurement of measurable/non-measurable and target/non-target lesions and lymph nodes are in line with RECIST 1.1.

One new definition is added: If a subject has no measurable and no non-measurable disease at baseline the radiologist will assign 'No Disease' (irND) as the overall tumor assessment for any available follow-up time points unless new measurable lesions are identified and contribute to the total measured tumor burden (TMTB). irND is a valid assessment in studies with adjuvant setting where the protocol and study design allow the inclusion of subjects with no visible disease

Follow-up Assessments in irRECIST

A. Follow-up recording of target and new measurable lesions

The key difference in irRECIST is that the appearance of new lesions does not automatically indicate progression. Instead, all measured lesions (baseline-selected target lesions and new measurable lesions) are combined into the total measured tumor burden (TMTB) at follow up. Baseline-selected target lesions and new measurable lesions are NOT assessed separately. Measurements of those lesions are combined into the TMTB, and one combined assessment provided.

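### Objective II relates blood-marker trend groups to PFS and OS from treatment start with no trend window or landmark, so groupings that depend on series length can carry guarantee-time bias

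*Combined protocol and SAP*

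**What the plan says.** Section 14.2, objective II, describes the trend grouping: "their trends over time will be categorized either by visual inspection (if there are clear trend groups such as monotonically increasing or monotonically decreasing", with pattern-recognition methods such as K-means as the alternative. The groups are then related to PFS and survival by methods that include Kaplan-Meier curves and Cox models.

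Both endpoints start at the first treatment. Section 12.10: "PFS is defined as the period from start of study treatment until recurrent or progressive of disease (POD) is objectively documented". Section 12.11: "OS is defined as the observed length of life from start of study treatment to death or the date of last contact".

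The marker data come later. Section 10.3: "Blood samples for research purposes will be obtained at week 1, 4, 7, 13, 19, 22 and at the date of the off study visit". The last sample is tied to the end of treatment (Table 6, footnote 10): "The off study visit will take place 30 days (+7 days) after the last dose". Progression is looked for on a fixed calendar (section 10.2): "Imaging studies will be performed at baseline, week 8 and every 8 weeks subsequently".

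Dosing, and with it scheduled sampling, may run past first progression. Section 4.1: "dosing should continue provided that the subject has no evidence of confirmed PD within 8 weeks of initial PD per RECIST". Section 9.2: "The patient may be allowed to continue study treatment after initial RECIST 1.1 defined progression".

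For objective II the plan gives no window for the trend, minimum number of samples, landmark or time-dependent covariate. Objective III, in the same section, does specify a landmark Kaplan-Meier curve for the change between pre- and post-treatment tissue.

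**The concern.** The grouping uses data collected after the time origin, and how much data a patient contributes depends on the outcome. A patient who progresses early leaves treatment early and has a short series. A short series is more likely than a long one to rise or fall throughout. Any grouping in which series length matters (monotone against not, or rising, falling and neither) therefore puts more early progressors in the monotone group, even when the marker has nothing to do with outcome. Comparing PFS from treatment start between such groups can make that marker look prognostic, with the monotone group looking worse.

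Section 14.2 intends these results to help identify patients who may benefit and to inform phase III design, and section 2.0 repeats the blood-marker objective for the additional cohorts. Being exploratory excuses low power. It does not excuse a bias in a known direction.

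**Working it through.** The plan gives no figure for this analysis, so there is nothing to reproduce. The check counts samples, works out the chance of a monotone series, and simulates the comparison under no association.

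**Inputs from the plan.** In weeks elapsed since first treatment, scheduled samples fall at 0, 3, 6, 12, 18 and 21. Scans fall at 7, 15, … 55, then every 12 weeks. Doses are 3 weeks apart, and the off-study sample is 30 days after the last dose. The initial cohort has 20 patients.

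**Assumptions, not in the plan.** The marker is a random walk independent of outcome. PFS is exponential with median 12, 16 or 24 weeks, detected at scans and censored at 75 weeks. Post-progression survival is exponential with median 40 weeks, followed for 52 weeks. Sampling runs either 0 or 8 weeks past progression. The test is a log-rank at nominal 5%. A trial is testable if each group has at least 2 patients. There were 3,000 trials per setting at n=20.

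**Step 1: samples per patient.**
- Dosing for 8 weeks past progression. Progression at the week-8 scan: 7 + 8 = 15 weeks, so samples at 0, 3, 6 and 12 plus off-study = 5. Progression at the week-16 scan: 15 + 8 = 23 weeks, so 6 + 1 = 7. Still on treatment: 6.
- Dosing stops at progression. Week-8 scan: 3 + 1 = 4. Week-16 scan: 4 + 1 = 5. Week-24 scan: 6 + 1 = 7.

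**Step 2: chance that a series of k samples is monotone.** For a random walk this is 2 × (1/2)^(k−1): 25% for k=4, 12.5% for k=5, 6.25% for k=6 and 3.1% for k=7. For independent noise it is 2/k!: 8.3% for k=4, 1.7% for k=5 and 0.04% for k=7. The direction is the same under both models.

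**Step 3: false positives, monotone against not, n=20 (median PFS 12/16/24 weeks).**

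| Setting | Rate in testable trials | Testable | Rate in all trials |
|---|---|---|---|
| Sampling 8 weeks past progression, off-study sample counted: PFS | 24.0/23.1/22.4% | 35.9/30.1/29.7% | 8.6/7.0/6.7% |
| Same setting: OS | 15.9/13.1/13.6% | – | – |
| Scheduled sampling stopped at progression, off-study sample counted: PFS | 32.4/38.0/37.2% | 75.1/65.9/55.0% | 24.3/25.0/20.5% |
| Same, off-study sample left out: PFS | 54.0/54.7/53.1% | – | – |

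The last column is the product of the two before it, for example 0.324 × 0.751 = 0.243. In the first setting, patients progressing at the first scan make up 65/57/43% of the monotone group but 33/26/18% of all patients. Permuting the group labels in that setting brings the conditional rate down to 6–8%, so the excess does not come from small groups. Rising, falling or neither (at least 1 per group) gives 11.5/19.1/28.6%, testable in 21.8/16.8/18.0%.

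**Step 4: groupings that are not inflated (first setting).** Slope sign gives 6.5/5.8/6.2%. K-means with two clusters and last value carried forward gives 5.5/6.3/6.6%. Rising against falling does not depend on series length when steps are symmetric, and is testable in only about 1% of trials.

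**Step 5: larger samples (first setting, 1,500 trials each).** n=30 gives 26.7/26.4/24.5%, testable in 54.5/51.3/47.4%. n=50 gives 29.6/26.6/23.4%, testable in 83.5/79.7/76.0%. These apply only if the additional cohorts are pooled, which the plan does not state.

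**Step 6: with a landmark.** Monotone against not, trend and follow-up split at week 7: 5.2/6.3/6.2%, all trials testable. At week 13: 5.7/6.7/7.1%, testable in 86/92/93%.

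**The case against.** The inflated contrast is one the plan permits but does not name. Its two stated routes are visual grouping when clear trend groups exist, with rising and falling as examples, and clustering. Neither rising against falling nor K-means with last value carried forward is inflated. The list of survival methods is open-ended and does not rule out a landmark, which the authors use for objective III.

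The practical size is also limited. In the first setting only about a third of trials at n=20 have enough monotone patients to test, and the false-positive rate over all trials is 7–9%, against 5–6% with a week-7 landmark. The random walk is an assumption. With a mean-reverting marker (autocorrelation 0.5 or 0.8) the contrast is testable in 3–5% or 11–17% of trials, and the all-trial rate falls to 1–2% or 4–5%. With independent noise it is testable in under 1%. Within a single histology cohort of 10 it is testable in 10–13%, with under 2% false positives overall.

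All of this stands as a limit on size and supports a minor grade. It does not remove the point. The examples are introduced as examples, so a remaining group of patients with no clear trend is a natural third category. Among testable trials with the mean-reverting marker the rate stays at 29–48%. If scheduled sampling stops at progression, the random-walk contrast is testable in more than half of trials. Nothing in the plan prevents the biased version, and choosing groups by eye after seeing the curves leaves the choice open.

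**Conclusion.** The concern holds, as a minor point. Objective II lets a post-baseline grouping whose content depends on follow-up be compared on PFS and OS from treatment start. For groupings that depend on series length, a marker unrelated to outcome is falsely associated with PFS in 22–24% of testable trials (7–9% of all) when sampling runs 8 weeks past progression. The figures are 32–38% (20–25% of all) when scheduled sampling stops at progression. For OS the first setting gives 13–16% of testable trials.

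These sizes rest on the random-walk marker, the assumed PFS and survival distributions, and 20 patients. The direction rests only on early progressors having shorter series. Groupings that do not depend on series length are not affected, nor are the primary endpoint and the toxicity stopping rule.

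**What to change.** In section 14.2, objective II, prespecify a landmark, for example week 7 or week 13. Define the trend only from scheduled samples up to that week and leave out the off-study sample, whose timing depends on when treatment ended. Analyze PFS and OS from the landmark in patients still event-free and in follow-up. Alternatively, enter the marker as a time-dependent covariate in a Cox model from treatment start. Whichever is chosen, state the minimum number of samples a patient needs.

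The change costs some wording and slightly different code, with no new data. Patients with an event before the landmark drop out of that analysis. In the simulation a week-13 landmark loses on average 3.7 of 20 patients at median PFS 24 weeks and 6.7 at 12 weeks. A week-7 landmark loses none if progression is found only at scheduled scans, though any earlier death or clinical progression would be lost. It rests on three samples, where half of random-walk series are monotone (2 × (1/2)² = 50%), so the trend says less.

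### Objective III gives the week-8 biopsy change a landmark for Kaplan-Meier but not for Cox, so progression already present at biopsy can appear to be predicted by it

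*Combined protocol and SAP*

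**What the plan says.** Section 14.2, objective III, treats two quantities differently.

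- Pre-treatment value: "Kaplan-Meier curve and Cox Proportional Hazards models will be used for analyzing pre-treatment measurement". This is sound, because the value is known on day 1.
- Pre/post difference: "Kaplan-Meier curve at a landmark time point and Cox Proportional Hazards models allowing for time varying coefficients".

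No landmark time is given. For the Cox model, no section states a landmark, a later time origin, delayed entry, a time-dependent covariate, or an exclusion of events at or before the biopsy.

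The endpoint definitions start the clock on day 1. Section 12.10: "PFS is defined as the period from start of study treatment until recurrent or progressive of disease (POD) is objectively documented". Section 12.11: "OS is defined as the observed length of life from start of study treatment to death or the date of last contact".

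Section 10.2 sets the scans: "Imaging studies will be performed at baseline, week 8 and every 8 weeks subsequently", with a one-week window. Table 6, footnote 5, puts the on-treatment biopsy at week 8 ± 7 days. Sections 4.1, 9.2 and 12.1 let selected patients continue treatment after a first RECIST progression.

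Section 14.1 calls the biopsy correlatives exploratory. Section 14.2 says that they are not powered, but also that they should help to identify patients likely to benefit and to design Phase III studies.

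**The concern.** The pre/post difference does not exist until the second biopsy has been taken. An analysis that starts on day 1 and carries the difference as a covariate uses a later measurement to explain earlier events. The plan guards against this for the Kaplan-Meier curve. For the Cox model it names a device for a different problem, non-proportional hazards.

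This matters here because the first scheduled progression assessment falls in the same two-week window as the biopsy. A tumour that is already growing may have a different immune infiltrate because it is growing. If that patient's progression counts as an event, the consequence of progression is read as its predictor, and a marker could be carried forward for patient selection on that basis.

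**Working it through.** The plan gives no sample size, event count, alpha or power for objective III, so there is no stated figure to reproduce. The check is of the model, then the calendar, then size under stated assumptions.

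**1. The model.** Let Z be the post-minus-pre difference. A Cox model with a time-varying coefficient is h(t) = h0(t) exp{β(t)Z}. Each event time t contributes exp{β(t)Z_i} / Σ exp{β(t)Z_j}, summed over everyone at risk at t. Z is the same number at every t; only β moves. A landmark model at time L keeps only event times after L and patients event-free at L.

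**2. The calendar.** Earliest scan: week 8 − 7 days. Latest biopsy: week 8 + 7 days. A progression can be dated up to 7 + 7 = 14 days before Z exists. Such a patient can still be biopsied, because treatment past first progression is allowed.

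**3. Which endpoint.** A patient with a Z value was alive at biopsy, so no death in this data set precedes that patient's own biopsy. The artefact is therefore mainly one of PFS. For OS the issue is mainly guaranteed survival up to the biopsy.

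**4. How many patients.** Assume exponential PFS with median m weeks. The share progressing by week 8 is 1 − 2^(−8/m): 50% for m = 8, 29% for m = 16, 21% for m = 24. With independent ±7-day windows, about half of those scans fall on or before the biopsy date (44%-50% in simulation).

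**5. Size.** None of these inputs is in the documents: the progression rates, the marker shift in tumours already progressing at biopsy, and (in B) 80% of first-scan progressors still biopsied. There is no true effect on later progression, and tests are at nominal 5%. The 50 patients are 20 + 3 × 10, which assumes pooling and complete biopsy pairs.

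- A: 40% progress at week 8; scans every 8 weeks to week 48; one time-by-marker term; 600 runs.
- B: medians of 8, 16 and 24 weeks; coefficient with a step at week 9, 2-df test (critical value 5.991); 400 runs (n = 20) or 250 (n = 50).
- C: as A for progression and shift, with independent ±1-week windows.

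| Model from day 1 unless stated | Shift | n = 20 | n = 50 |
|---|---|---|---|
| Time-varying coefficient, A | 1 SD | 13% | 51% |
| Time-varying coefficient, B | 1 SD | 28%-36% | 58%-78% |
| Time-varying coefficient, C | 1 SD | 38% | – |
| Time-varying coefficient, A | 0.5 SD | 5% | 9% |
| Time-varying coefficient, B | 0.5 SD | 10%-14% | 16%-25% |
| Time-varying coefficient, B | none | 5%-7% | 4%-5% |
| Constant coefficient, A | 1 SD | 13% | 38% |
| Constant coefficient, B | 1 SD | 15%-31% | 24%-63% |
| Entry at own biopsy date, B | 1 SD | 9%-15% | 13%-36% |
| Covariate switched on at biopsy, C | 1 SD | 14% | 25% |
| Landmark, A | 1 SD | 3% | 3% |
| Landmark at week 9, B | 1 SD | 7% | 5%-9% |
| Landmark, C | 1 SD | 6% | 4% |

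In B with a 1 SD shift, the hazard ratio per SD is 0.43-0.56 up to week 9 and 0.93-0.99 afterwards. The artefact sits almost wholly in the early segment.

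The landmark is close to nominal, not exact. Its highest rate in B is 8.8%. The simulation standard error is √(0.05 × 0.95 / 250) = 1.4 points, so that rate is (8.8 − 5)/1.4 = 2.7 standard errors above 5%. It is the highest of 18 settings. A small residue is also plausible: a patient with a clear scan in week 7 may be progressing at a week-9 biopsy and be detected only at the next scan.

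**The case against.** The authors plainly saw that the difference needs separate handling. The word coefficients may be a slip for covariates, or the landmark may have been meant to govern both methods. A coefficient fixed at zero up to week 9 and constant afterwards is, formally, a time-varying coefficient, and it gives the landmark partial likelihood exactly. The day-1 origin of the Cox model is inferred from the PFS and OS definitions; objective III does not state it.

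All of that is fair. A reader might infer that the plan declares the change known from day 1, and the documents do not say so. But each kind reading needs words that are absent: a landmark time, its extension to the Cox model, or a form for β(t). If covariates was meant, part of the problem remains, because progression present at biopsy and scanned days later would still be predicted (9%-36% rejection in B, 14% and 25% in C).

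A reader might also blame the extra parameter in a small data set. With 20 patients, A gives 12.7% for a constant coefficient and 13.0% for a time-varying one, so there the early origin does the damage. The time-varying form adds to it in other settings, but it is not the root.

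**Conclusion.** Wrong as written, and minor. Followed literally, the Cox half of the sentence lets progressions found at or before the week-8 biopsy be explained by a value measured at or after them.

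The direction follows from the text and the calendar, given the inferred day-1 origin. The size does not. A reader might take 13%-38% or 51%-78% as the plan's error rates, but the documents give neither the progression rate at week 8 nor any marker shift. The figures also vary widely with the assumed form of β(t) and the scan timing. With no shift there is no inflation, and with 0.5 SD and 20 patients it may be nil. The 50-patient figures also need pooled cohorts and complete pairs; no section specifies pooling, and Section 10.3 takes biopsies where feasible.

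Nor does the point reach the trial's efficacy or safety conclusions. The primary and secondary endpoints do not use this model, and no decision rule depends on it.

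**What to change.** In objective III, drop the time-varying-coefficient wording for the pre/post difference. Specify instead a Cox model starting from one fixed landmark at the end of the week-8 biopsy and scan window (week 8 + 7 days, for example week 9). Use the same landmark for the Kaplan-Meier curve. For PFS, include only patients alive and progression-free at the landmark; for OS, those alive then. Report how many are excluded and why.

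Do not list a covariate that switches on at the biopsy date as an equivalent for PFS.

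The cost is one sentence and the matching code. The downside is fewer patients in the PFS model: under the assumed medians, 21%-50% progress at the first scan, or about 4 to 10 of 20 (0.21 × 20 = 4.2; 0.50 × 20 = 10). Those with paired biopsies stay in the comparison of marker change by response, which objective III already plans.
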